2.4. Sample Size Determination

The sample size of 210 subjects who undergo implantation and exchange of a Travoprost Intraocular Implant was determined to support the study objectives and is not based on statistical power calculations. [REDACTED]

[REDACTED]

3. Analysis Sets

For the purposes of analysis, the following analysis set is defined:

Subject Analysis Set	Description
Safety analysis set	
• All subjects who receive an implant.

The safety analysis set will be used for all data tabulations and listings.

4. General Statistical Considerations

Demographic and safety data collected on the case report forms (CRFs) will be displayed in tabulations and data listings. Only data from scheduled visits will be used in tabulations unless otherwise specified. In general, summary tables will be presented [REDACTED] [REDACTED]. Data may also be summarized by study period if indicated. Data listings will present data either recorded on or derived using the CRF. [REDACTED] [REDACTED]

No formal statistical testing will be performed. All data summaries [REDACTED] will be performed using SAS® software, Version 9.4 or higher.

Continuous data will be summarized using the number of observations, mean, standard deviation, median, minimum, and maximum. Continuous data may also be dichotomized, or otherwise split, into clinically meaningful categories and may be further analyzed as categorical data as specified in the individual endpoints.

Categorical data will be summarized using frequency counts and percentages. Unless otherwise stated, subjects with missing visit data will be omitted from both the numerator and denominator of such calculations.

4.1. Definition of Variables

4.1.1. Baseline Measure

The baseline measure is defined as the last non-missing measure prior to the implantation of the 1st Travoprost intraocular implant at Visit 2 (First Operative Day 0).

4.1.2. Pre-Exchange Measure

The pre-exchange measure is defined as the last non-missing measure prior to the implantation of the 2nd Travoprost intraocular implant at Visit 7 (Second Operative/Exchange).

4.1.3. Change from Baseline/Pre-Exchange

The change from baseline (CFB) and the change from pre-exchange (CFPE) values are calculated as

- CFB value = follow-up visit value – baseline value.
- CFPE value = follow-up visit value – pre-exchange value.

4.1.4. Study Days

Two sets of study days are defined and will be referred to as the initial and PE study days. The number of initial study days is defined relative to the First Operative visit (Visit 2), with the First Operative visit as study day 1. The number of PE study days is defined relative to the Second Operative visit (Visit 7), with the Second Operative visit as study day 1. For both sets of study days, the study day value increases by 1 for each date following the corresponding Operative visit. For each date prior to the corresponding Operative visit, the study day value decreases by 1, with the date preceding the Operative visits as study day -1.

5. Demographic and Baseline Characteristic Analyses

5.1. Subject Disposition

The number and percentage of subjects who were screened, screened but not enrolled (i.e., screen failures), and enrolled will be provided. A subject is considered enrolled at the time the subject undergoes surgery at the First Operative visit (Visit 2). Reason(s) for screen failure will also be presented in a table and subject listing.

Subject disposition will be summarized [REDACTED] for all enrolled subjects. The summary will include the number and percentage of subjects who completed the study and the number and percentage of subjects who exited early (with reasons for study exit) prior to the Week 4 PE examination. The reasons for early study exit include:

- Adverse Event
- Death
- Investigator Decision
- Lost to Follow-up
- Termination of Study by Sponsor or Regulatory Authority
- Withdrew Consent
- Other

Subject disposition will also be summarized [REDACTED] for the initial and PE study periods. The summary will include the number and percentage of subjects who completed the respective study period and the number and percentage of subjects who exited early (with reasons for study exit) during the respective study period.

Subject disposition and exit status will be listed by subject.

5.2. Protocol Deviations

Protocol deviations will be captured by the site and reviewed by a medical monitor during the study. Classification of major deviations will be decided by the study team prior to the database lock. For the safety analysis set, a summary of protocol deviations will be tabulated [REDACTED] [REDACTED] for the initial, PE, and total study periods. A listing of all protocol deviations will be provided.

5.3. Demographic and Baseline Characteristics

Subject demographics and baseline characteristics will be tabulated [REDACTED] for the safety analysis set. Demographic variables include age, sex, race, ethnicity, and eye color. Age will be calculated for each subject by $(\text{Informed Consent Date} - \text{Date of Birth}) \div 365.25$ and rounded down to the nearest integer. In addition to being summarized continuously, age will be summarized categorically for the following age groups: < 65 and ≥ 65 years of age.

The following baseline characteristics will be summarized [REDACTED] for the study eye:

- Type of Disease (OAG or OHT)
- Number of Ocular Hypotensive Medication Classes
- Medication Class

- IOP (mmHg)
- Best Spectacle Corrected Visual Acuity (BSCVA) - LogMAR
- Vertical Cup-to-Disc Ratio
- Corneal Thickness (μm)
- Shaffer Angle Grade
- Study Eye (OD or OS)

Demographic and baseline characteristic data will be listed.

5.4. Medical and Surgical History

All medical and surgical history will be coded to the Medical Dictionary for Regulatory Activities (MedDRA) nomenclature, Version 21.0. Medical and surgical history will be tabulated by System Organ Class (SOC) and preferred term (PT) [REDACTED]. Separate tabulations will be provided for study eye, non-study eye, and non-ocular histories. Subjects with more than one medical history within a given SOC or PT will only be counted once within that SOC or PT. Ocular and non-ocular medical and surgical history will be listed.

5.5. Prior and Concomitant Medications

Prior medications are defined as those medications taken within 30 days prior to the start of Screening with a stop date prior to study drug administration. Concomitant medications are defined as those medications taken (1) prior to study drug administration and continuing for any period of time following the first administration of study drug or (2) at any time following the first administration of study drug.

Medications will be coded using the World Health Organization (WHO) Drug Dictionary (Version MAR2018) and will be summarized to the anatomical therapeutic chemical (ATC) class and preferred name. The number and percentage of subjects on medications will be tabulated by ATC, preferred name, [REDACTED]

- Prior medications in the study eye
- Prior medications in the non-study eye
- Non-ocular prior medications
- Concomitant medications in the study eye for the initial, PE, and totally study periods
- Concomitant medications in the non-study eye
- Non-ocular concomitant medications

Subjects will be counted only once under each ATC class or preferred name for which they have at least one medication. All prior and concomitant medications will be listed.

5.6. Concurrent Ocular Procedures

Concurrent ocular procedures are defined as any ocular procedures that occurred in the study eye on or after the date of the First Operative visit at Visit 2. Ocular procedures will be coded using the MedDRA nomenclature, Version 21.0. Ocular procedures will be tabulated by SOC, PT, [REDACTED] [REDACTED] for each study period. Subjects with more than one ocular procedure within a given SOC or PT will only be counted once within that SOC or PT. All concurrent ocular procedures will be listed.

6. Efficacy Analyses

6.1. Primary Endpoint Efficacy Analysis

There are no primary efficacy endpoints in this study.

6.2. Secondary Endpoint Efficacy Analysis

There are no secondary efficacy endpoints in this study.

6.3. Exploratory Endpoint Efficacy Analysis

There are no exploratory efficacy endpoints in this study.

7. Safety Analyses

All safety analyses will be based on the safety analysis set and will be described in more detail in the following sections.

7.1.1. Extent of Exposure

Summaries of the extent of exposure to study treatment, which include the number of participants exposed and descriptive statistics of the duration of exposure in study days, will be provided [REDACTED] for each study period. Extent of exposure to study treatment in days will be calculated differently by study period. For the total study period, extent of exposure will be calculated as date of study exit – date of 1st Operative visit + 1. For the initial study period, extent of exposure will be calculated as date of 2nd Operative visit – date of 1st Operative visit + 1. For the PE study period, extent of exposure will be calculated as date of study exit – date of 2nd Operative visit + 1. If the date of study exit, or the date of 2nd Operative visit for the initial study period, is missing for a subject with early study exit, the date of the last recorded visit will be used for calculations. A listing of extent of exposure will be provided.

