7.1.2. Adverse Events

Adverse events (AEs) will be coded to the MedDRA nomenclature, Version 21.0. Treatment Emergent Adverse Events (TEAEs) are defined as AEs that occur after the initiation of the first surgery at Visit 2 (First Operative Day 0).

AEs will be categorized into either the initial or PE study periods, as described in Section 2.3.1. AEs that extend between study periods (i.e., beginning during the initial study period and extending into the PE study period), will be categorized into the initial study period. However, if an increase in severity or change in relationship to study treatment occurs during the PE study period, the AE will be categorized into both the initial and PE study periods.

A summary of the number and percentage of subjects with TEAEs [REDACTED] will be provided for each study period. The summary will include study eye TEAEs, non-ocular or non-study eye TEAEs, treatment-related TEAEs, TEAEs by maximum severity, TEAEs resulting in study discontinuation, serious TEAEs, and deaths.

The number and percentage of subjects with study eye TEAEs, non-study eye TEAEs, and non-ocular TEAEs will be provided by SOC, PT, [REDACTED] for:

- TEAEs
- TEAEs related to study treatment
- TEAEs by maximum severity
- Serious TEAEs

Tabulations of study eye TEAEs for each of the above categories will be provided for each study period.

All AEs will be presented in a listing by subject. Separate listings for intraoperative AEs, serious adverse events (SAEs), AEs leading to deaths, AEs leading to study discontinuation, and AEs leading to removal of implant will also be presented.

Relationship to study treatment is defined as the possibility that the study treatment caused the event and is described in the study protocol. The relationship to study treatment categories utilized on the CRF are definitely unrelated, unlikely related, possibly related, probably related, and definitely related. For all tabulations presenting relationship to study treatment, the categories of possibly related, probably related, and definitely related will be classified as related and only related AEs will be presented. AEs with missing relationships are counted as related. Subjects experiencing more than one treatment related AE within a given SOC or PT will be counted once within that SOC or PT.

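### SAP 7.1.1 can give a subject who exits before exchange two lengths for one implant exposure, and has no end date for implant removal without replacement

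*SAP*

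**What the plan says.** SAP 7.1.1 (Extent of Exposure) gives three formulas and one fallback rule. A redaction in that section falls in the sentence on how the summaries are presented; the formulas are fully visible.

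- Total period: "For the total study period, extent of exposure will be calculated as date of study exit – date of 1st Operative visit + 1".
- Initial period: "extent of exposure will be calculated as date of 2nd Operative visit – date of 1st Operative visit + 1".
- Post-exchange (PE) period: "extent of exposure will be calculated as date of study exit – date of 2nd Operative visit + 1".
- Fallback: if the exit date, or for the initial period the 2nd Operative date, "is missing for a subject with early study exit, the date of the last recorded visit will be used for calculations".

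No formula refers to the date on which an implant was taken out: in both the total and PE periods, "extent of exposure will be calculated as date of study exit". SAP 7.1.2 (Adverse Events) nevertheless plans separate listings of "AEs leading to study discontinuation, and AEs leading to removal of implant will also be presented".

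Four other places bear on this:

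- SAP 2.3.1 (Study Period) puts everything collected before the exchange in the initial period, and data from the exchange procedure in the PE period.
- Protocol 6.2.3.2 (After Implantation) permits exit for a potentially harmful condition but does not require it. It does not mention implant removal.
- Protocol 6.2.3.3 (Lost to Follow-up) requires at least three telephone attempts, then a letter and a week's wait, before the Study Exit form is completed.
- SAP 5.6 (Concurrent Ocular Procedures) lists every study-eye procedure from the first operation onward.

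**The concern.** The section describes exposure to study treatment, and the treatment is a drug-eluting implant. A reader will take the table as the time that study eyes carried one. On the stated rules, two kinds of subject can get entries that do not mean this.

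**(a) Exit before exchange.** Under SAP 2.3.1 such a subject has only an initial period, so initial and total exposure should be equal. The fallback replaces the missing 2nd Operative date with the last visit, but leaves the total period running to the exit date if one is recorded. The days between belong to the total and to neither component period.

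**(b) Removal without replacement, subject still followed.** Exposure continues to accrue with no implant in the eye.

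At stake is the accuracy of a planned safety table that sits beside adverse-event tables for groups exchanged from Month 3 to Month 24. The SAP gives no other summary of time on treatment.

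**Working it through.** **Inputs.** First operation is day 0. Nominal exchange days run from 91 (Group 3) to 730 (Group 24), from Protocol 6.3.4.7. Week 4 PE is 28 days after exchange (Protocol 6.3.4.10). One month is taken as 365.25/12 = 30.44 days. Write L for last recorded visit, X for study exit and R for removal.

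**Reproducing the plan's own figure.** Protocol Section 7 gives a total duration of 4 to 25 months. The total formula gives:

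- Group 3: 91 + 28 + 1 = 120 days = 3.94 months
- Group 24: 730 + 28 + 1 = 759 days = 24.94 months

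The formula therefore behaves as intended for completers.

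**(a) Never exchanged, exit date recorded.** Initial = L + 1 and total = X + 1, so total − initial = X − L. The dates below are assumed.

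| L (day) | X (day) | Initial | Total | Gap |
|---|---|---|---|---|
| 28 | 28 | 29 | 29 | 0 |
| 365 | 372 | 366 | 373 | 7 |
| 365 | 395 | 366 | 396 | 30 |
| 365 | 589 | 366 | 590 | 224 |
| 365 | missing | 366 | 366 | 0 |

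Day 589 is Month 18 plus its window plus an assumed 28 days of contact attempts: 547 + 14 + 28. This row applies to Groups 21 and 24, which have an interim Month 18 visit. Long gaps between visits are not special to those groups: Month 6 to Month 12 is 365 − 182 = 183 days in Groups 15 and 18 as well.

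A gap above zero is the expected case for a subject lost to follow-up, because the exit form is completed only after the contact attempts and the wait.

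**(b) Removal without replacement.** Time in situ is R + 1. The excess is X − R for the total period and L − R for the initial period. With an assumed removal on day 182 (183 days in situ):

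| L (day) | X (day) | Initial (excess) | Total (excess) |
|---|---|---|---|
| 182 | 182 | 183 (0) | 183 (0) |
| 365 | 365 | 366 (183) | 366 (183) |
| 365 | 395 | 366 (183) | 396 (213) |

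**Exchange day.** For exchanged subjects, initial + PE = total + 1, because the exchange day is in both: 92 + 29 = 121 against 120 in Group 3, and 731 + 29 = 760 against 759 in Group 24.

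**The case against.** **Nothing planned depends on the table.** The adverse-event tables give counts and percentages of subjects, and no rate per unit of exposure is planned. This stands and limits the point to the exposure table and listing. A reader might infer that event rates are biased downward, but the SAP plans no such rates.

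**Exposure to study exit matches the adverse-event window.** Protocol Section 9 records events to the final visit, and SAP 7.1.2 sets no cut-off at removal. Shortening exposure alone would create a new mismatch. This also stands, and it is why the present formula should stay as a follow-up row.

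**Continued follow-up without an implant is not a planned situation.** A reader might infer from the separate removal listing in SAP 7.1.2 that it is. That does not follow: the listings overlap by nature, since an event leading to death is also serious. No schedule covers such a subject, and SAP 2.3 has every enrolled subject undergo exchange. What remains is that no passage excludes it. One can construct a Group 24 subject with removal on day 182, a last visit on day 730 and exit on day 758, giving 731 initial days against 183 in situ. That roughly four-fold figure is a hypothetical worst case and no measure of the likely effect.

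**One end date at exit credits unobserved time to subjects lost to follow-up.** True, but the total period already does so. Ending both periods at the last visit would also be consistent.

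**The exchange-day overlap is a convention.** Agreed. SAP 4.1.4 makes each operative visit day 1 of its own count, and the SAP never says that the periods sum. A reader might infer that the table fails to add up in a material way for completers, but the difference is 1 day.

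**Conclusion.** The concern holds at minor severity. Both effects follow from the formulas as written, and both are conditional.

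- **Two end dates.** The gap is exit minus last visit. It needs a subject who leaves before exchange and whose recorded exit date is later than the last visit. I assume that the exit date on the form reflects the end of the contact process; if sites enter the last visit date, the gap is 0.
- **Removal.** The excess in the total period is exit minus removal. It needs removal without replacement followed by continued participation, and is 0 if the subject exits that day.

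The documents give neither the number of early exits nor the number of removals, so the effect on the table's means and medians cannot be computed. No test, sample size or planned rate is affected.

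**What to change.** Amend SAP 7.1.1 as follows.

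1. For subjects never exchanged, end the initial and total periods on the same date: study exit, or the last recorded visit if the exit date is missing.
2. End implant exposure at removal without replacement if that comes earlier.
3. Keep the present formula as a separate row labelled follow-up time, so that a figure matching the adverse-event window remains.
4. Optionally, count the exchange day once, in the PE period, in line with SAP 2.3.1. Completers then add up: 91 + 29 = 120 in Group 3 and 730 + 29 = 759 in Group 24.

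This is an analysis definition only; it takes no position on when an implant should be removed or a subject exited.

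The cost is a few sentences and minor programming before database lock. Operative, exit and visit dates already feed the formulas. The documents do not say that a removal date is recorded, so the sponsor should confirm that it is, for example as a concurrent ocular procedure under SAP 5.6. Reported exposure will change slightly for the subjects concerned: the initial period lengthens in case (a), and exposure shortens in case (b).

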7.1.2. Adverse Events

Adverse events (AEs) will be coded to the MedDRA nomenclature, Version 21.0. Treatment Emergent Adverse Events (TEAEs) are defined as AEs that occur after the initiation of the first surgery at Visit 2 (First Operative Day 0).

AEs will be categorized into either the initial or PE study periods, as described in Section 2.3.1. AEs that extend between study periods (i.e., beginning during the initial study period and extending into the PE study period), will be categorized into the initial study period. However, if an increase in severity or change in relationship to study treatment occurs during the PE study period, the AE will be categorized into both the initial and PE study periods.

A summary of the number and percentage of subjects with TEAEs [REDACTED] will be provided for each study period. The summary will include study eye TEAEs, non-ocular or non-study eye TEAEs, treatment-related TEAEs, TEAEs by maximum severity, TEAEs resulting in study discontinuation, serious TEAEs, and deaths.

The number and percentage of subjects with study eye TEAEs, non-study eye TEAEs, and non-ocular TEAEs will be provided by SOC, PT, [REDACTED] for:

- TEAEs
- TEAEs related to study treatment
- TEAEs by maximum severity
- Serious TEAEs

Tabulations of study eye TEAEs for each of the above categories will be provided for each study period.

All AEs will be presented in a listing by subject. Separate listings for intraoperative AEs, serious adverse events (SAEs), AEs leading to deaths, AEs leading to study discontinuation, and AEs leading to removal of implant will also be presented.

Relationship to study treatment is defined as the possibility that the study treatment caused the event and is described in the study protocol. The relationship to study treatment categories utilized on the CRF are definitely unrelated, unlikely related, possibly related, probably related, and definitely related. For all tabulations presenting relationship to study treatment, the categories of possibly related, probably related, and definitely related will be classified as related and only related AEs will be presented. AEs with missing relationships are counted as related. Subjects experiencing more than one treatment related AE within a given SOC or PT will be counted once within that SOC or PT.

Severity is a measure of intensity and is graded on a 3-point scale as outlined in the study protocol. AEs will be rated as either mild, moderate, or severe. AEs with missing severities are counted as severe. For all tabulations, subjects experiencing more than one AE within a given SOC or PT will be counted once within that SOC or PT at the maximum severity.

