4.2 Safety

- Adverse events (intra-operative and post-operative adverse events [TEAEs]) in the study eye will be monitored.
- IOP, best spectacle corrected visual acuity, slit lamp biomicroscopy findings, gonioscopy findings, and ophthalmoscopy findings (including cup-to-disc ratio) will be assessed.
- Operative and Surgical Assessments will be collected.

CLINICAL PROTOCOL

Date:
September 18, 2019

Protocol No.:
IDOS-402-IVIV

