6.3.4 TREATMENT PROCEDURES

6.3.4.1 Visit 2 (First Operative Day 0)

- 1) Assess demographics, medical and surgical history, current ocular and systemic conditions, prescription medications, and medications known or suspected to lower IOP.
- 2) Assess any adverse events.
- 3) Prepare subject for surgery.

CLINICAL PROTOCOL

Date: September 18, 2019	Protocol No.: IDOS-402-IVIV
-----------------------------	--------------------------------

- 4) Administer an additional drop of antibiotic 30 minutes preoperatively.
- 5) Visually confirm Shaffer grade angle and target implant location.
- 6) Obtain a treatment kit.
- 7) Administer anesthetic (topical, general, retrobulbar, peribulbar).
- 8) Perform surgery.
- 9) Record clinical data from the surgical procedure on the First Operative Day 0 CRF, noting study eye intra-operative AEs and post-operative AEs.

Postoperatively:

- 10) Schedule the subject to return for Visit 3 (Day 1).
- 11) Dispense other postoperative medications and instruct the subject as follows:
[REDACTED]

[REDACTED]

[REDACTED]

[REDACTED]

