6.3.4.7 Visit 7 (Second Operative / Exchange Exam)

Depending on the cohort, the subject may have their Visit 7 (Second Operative / Exchange Exam) occur on one of the following visits (please see **APPENDIX A-G: SCHEDULE OF VISITS & MEASUREMENTS):**

CLINICAL PROTOCOL

Date:
September 18, 2019

Protocol No.:
IDOS-402-IVIV

(Month 12, 365 days ± 14)

(Month 3, 91 days ± 14)

(Month 6, 182 days ± 14)

(Month 24, 730 days ± 14)

(Month 21, 637 days ± 14)

(Month 18, 547 days ± 14)

(Month 15, 456 days ± 14)

- 1) Update subject's medical status and concomitant medications.
- 2) Assess study eye adverse events.
- 3) Prepare subject for surgery.
- 4) [REDACTED]

The following steps will be performed in the Operating Room:

- 5) Visually confirm Shaffer grade angle and target implant location.
- 6) Collect an anterior chamber aqueous humor sample (AC tap).
Please follow instructions in the procedure manual.

After collecting the AC Tap and performing all assessments:

- 7) Obtain a treatment kit.
- 8) Administer anesthetic [REDACTED]
- 9) Perform second surgery (Exchange).
- 10) Collect the first implant for shipment back to sponsor.
- 11) Record clinical data from the surgical procedure on the Second Operative CRF, noting study eye intra-operative AEs and post-operative AEs.
- 12) Schedule the subject to return for Visit 8 (Day 1 Post Exchange).

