8.5 Safety Analyses

8.5.1 ADVERSE EVENTS

Adverse events (AEs) in the study eye will be coded using the Medical Dictionary for Regulatory Activities (MedDRA) nomenclature. Treatment Emergent Adverse Events (TEAE) are defined as those AEs that occur after the initial treatment at Visit 2 (Operative Day 0).

AEs that occur on the date of the procedure are classified as either intra-operative or post-operative. Post-operative AEs are considered to be TEAEs. Intra-operative AEs and TEAEs will be summarized separately.

A line listing of serious adverse events will be provided.

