2.2. Endpoints

Safety Endpoints:

- Intraoperative adverse events
- Postoperative adverse events
- Intraocular pressure (IOP)
- Corrected visual acuity (logMAR score using ETDRS chart)
- Slit-lamp biomicroscopy findings
- Gonioscopy findings
- Ophthalmoscopy findings

Other:

- Operative and surgical assessments

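### The SAP counts intraoperative adverse events at the first implantation as TEAEs, the protocol keeps the two apart, and SAP section 10 declares no change

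*SAP*

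**What the plan says.** Protocol 8.5.1 has three sentences on this. TEAEs are "those AEs that occur after the initial treatment at Visit 2 (Operative Day 0". Next, "AEs that occur on the date of the procedure are classified as either intra-operative or post-operative". Then, "Post-operative AEs are considered to be TEAEs. Intra-operative AEs and TEAEs will be summarized separately".

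SAP 7.1.2 says that TEAEs "are defined as AEs that occur after the initiation of the first surgery at Visit 2 (First Operative Day 0". Its tables of all, related, maximum-severity and serious events are all tables of TEAEs. Intraoperative events are promised a listing of their own; no summary table for them is visible. SAP 2.2, however, gives "Intraoperative adverse events" as a safety endpoint in its own line, apart from postoperative events. SAP 2.3.1 assigns data collected during the exchange procedure to the post-exchange (PE) period. SAP 8.1.1, on operative and surgical analyses, is redacted. SAP section 10 states that nothing planned in the protocol was changed.

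**The concern.** The SAP starts the TEAE clock when the operation begins. The protocol describes TEAEs on an operation day as the events that follow the operation, with intraoperative events summarised apart from them. A programmer following the SAP would put a surgical complication at implantation into the TEAE counts; one following the protocol would not.

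At stake is what a TEAE percentage means. Under the SAP it mixes complications of surgery with events under the implant afterwards, so it is not the post-operative rate that the protocol describes. Because section 10 reports no change, nobody comparing the study report with the protocol is told that the definition moved.

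**Working it through.** The documents give one relevant design figure, 210 subjects (14 cohorts of 15; 14 × 15 = 210). It has no bearing on the definition. There is no planned event rate to reproduce, so the check is a comparison of texts followed by an illustration of size.

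**Step 1. An adverse event during the first implantation.**

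| Question | Protocol 8.5.1 | SAP 7.1.2 |
|---|---|---|
| Class | Procedure-day event, intra-operative | Begins after surgery has started |
| TEAE? | No: on that day the post-operative events are the TEAEs | Yes: no visible exclusion |
| Where counted | In a summary apart from TEAEs | In the TEAE tables for the initial and total periods, plus a separate listing |

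The two rules give different counts.

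**Step 2. An adverse event during the exchange.** Under the SAP it comes after the start of the first surgery, so it is a TEAE, and SAP 2.3.1 places it in the PE period. Under the protocol there are two readings. The first TEAE sentence of 8.5.1 takes in everything after treatment at Visit 2, which includes the exchange. The next two sentences separate intraoperative events from TEAEs but do not say which procedure they mean. Protocol 4.2 does not settle it: in "Adverse events (intra-operative and post-operative adverse events [TEAEs]) in the study eye will be monitored" the bracket can cover both kinds of event or only the second. The SAP conflicts with the protocol here on one reading and agrees with it on the other.

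**Step 3. The declaration.** Step 1 alone is a change from a protocol-planned analysis, so the SAP section 10 statement is incorrect whatever is decided about Step 2.

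**Step 4. Direction and size.** Adding a class of events to the definition cannot remove a subject from the count with at least one TEAE, so that percentage rises or stays the same. The same holds for related and serious TEAEs. In the maximum-severity table a subject may also move to a higher grade.

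For size, let p be the proportion with a post-operative event and i the proportion with an intraoperative event, over the same subjects. Both are assumptions. The SAP percentage is max(p, i) if the two groups overlap as fully as possible, 1 − (1 − p)(1 − i) if they are independent, and p + i if no subject has both.

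| p | i | Full overlap | Independent | No overlap |
|---|---|---|---|---|
| 10% | 2% | 10% | 1 − 0.90 × 0.98 = 11.8% | 12% |
| 10% | 5% | 10% | 1 − 0.90 × 0.95 = 14.5% | 15% |
| 10% | 10% | 10% | 1 − 0.90 × 0.90 = 19.0% | 20% |
| 20% | 1% | 20% | 1 − 0.80 × 0.99 = 20.8% | 21% |
| 20% | 5% | 20% | 1 − 0.80 × 0.95 = 24.0% | 25% |
| 20% | 10% | 20% | 1 − 0.80 × 0.90 = 28.0% | 30% |

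Under the protocol rule the TEAE percentage is p in every row. The excess runs from nil to i.

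**The case against.** The best defence is that little harm follows. The wider definition cannot hide a surgical complication. The SAP prints its definition, says openly that exchange-procedure data belong to the PE period, and lists intraoperative events separately, so a careful reader can take the two kinds apart. Protocol 8.1 presents the sample as informative about the safety of the exchange, and complications during that procedure are part of its safety. No formal testing of safety data is planned, so no inference depends on the count. The protocol's own wording is also loose.

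Much of this stands. It limits the consequence and rules out calling the exchange a clear conflict. It does not answer the first operation. A listing leaves the events inside the TEAE percentages, and the instruction to summarise the two apart would have little meaning if one already contained the other.

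Three stronger readings may tempt a reader; the documents do not support them.

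- That the intraoperative endpoint is never summarised. SAP 8.1.1 is redacted and could hold that table. If it does, the events would appear there and again among the TEAEs, so the overlap remains, but a missing summary cannot be claimed.
- That the SAP plainly contradicts the protocol at the exchange. Step 2 shows that the protocol allows either reading there.
- That PE-period percentages are diluted because all safety tables use all implanted subjects. The visible text does not say what number divides those percentages, wording beside those sentences is redacted, and numbers exposed and disposition by period are planned. That is a request for clarification, not a finding.

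**Conclusion.** The point holds as an undeclared conflict of definitions. At the first implantation the SAP counts intraoperative events as TEAEs and Protocol 8.5.1 does not, so SAP section 10 is wrong as written. This rests on the visible text of SAP 7.1.2, in which no exclusion appears. At the exchange the SAP takes the inclusive reading of an ambiguous protocol, and the rule should be settled in writing.

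The percentage of subjects with a TEAE can be too high relative to the protocol's definition, never too low. By how much cannot be derived: the percentages in the working rest on assumed rates and show only that the excess lies between nil and the intraoperative rate. No endpoint is lost.

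**What to change.** Amend SAP 7.1.2 before database lock so that TEAEs are limited to post-operative events, stated expressly for both the implantation and the exchange. Tabulate intraoperative events separately for each operation, unless the redacted SAP 8.1.1 already does so. Those tables need the same related, serious and maximum-severity breakdowns as the TEAE tables; otherwise narrowing the definition would take intraoperative events out of those breakdowns and put nothing in their place.

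Alternatively, keep the SAP definition and use section 10 to declare and justify the departure, saying how events during the exchange are treated.

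The cost is SAP wording and, for the first option, the intraoperative table shells. No new data are needed. At Visit 2 the site is already told: "Record clinical data from the surgical procedure on the First Operative Day 0 CRF, noting study eye intra-operative AEs and post-operative AEs". At Visit 7 the instruction is the same: "Record clinical data from the surgical procedure on the Second Operative CRF, noting study eye intra-operative AEs and post-operative AEs".
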